Appendix A : Disease burden and gaps.

Table 2. Primary and secondary prevention measures for food allergies^a

Trigg er	Primary prevention	Route of desensitization	Reference number	Secondary prevention	Refere nce number
Foods	Milk	PO, SL	(14;76-78)	Avoidance of allergenic food; education of allergic individuals and their care-givers on importance of avoidance, improved labeling of prepackaged foods for allergens, wearing of Medic-Alert bracelet stating specific food allergy	154,15 5
	Egg	PO	(11-13)		
	Peanut	PO	(39)		
	Tree nut	SL	(79)		
	Peach	SL	(80)		

^a only the most common foods , drugs and insect desensitization approaches are mentioned.

PO, **Per os**; SL, **Sublingual**; SC,

Table 2.Environmental factors associated with food allergy.

Factor	study	Type of study	Effect	Reference number
Season	Vassallo MF	Case control	Children younger than 5 years born in fall or winter had a 53% higher odds of food allergy compared with controls.	(81)
Drugs	Palli- Scholl	Case control	The relative risk to develop food-specific IgE after anti-acid therapy was 10.5 (95% CI,1.44,76.48).	(82)
Microbia l exposure	Gourbeyr e	Review of case control and cohort studies	No clear conclusion regarding probiotic beneficial effects on the prevention or treatment of allergy .	(83)
Food consumption (quantity and timing)	Poole JA	Cohort	After adjusting for breastfeeding duration, introduction of rice cereal, family history of allergy, and history of food allergy before 6 months of age, age at initial exposure to cereal grains continued to be strongly associated with wheat allergy (≥ 7 months: adjusted OR: 3.8; 95% CI, 1.18,12.28)	(84)

	Du Toit	Case control	After adjustment for atopy, other food allergies, age, and sex, the RR for peanut allergy in the UK vs Israel is 5.8 (95% CI, 2.8,11.8), and largest and most significant difference in weaning between the UK and Israel was observed in the age of introduction of peanut (P < .0001). By 9 months of age, 69% of Israelis were eating peanut compared with only 10% of UK infants.	(85)
	Katz	Cohort	The OR was 19.3 (95% CI, 6.0,62.1) for development of IgE mediated CMA among infants with exposure to cow milk protein at the age of 15 days or more (P < .001) vs those introduced to cow milk protein before 15 days.	(86)
	Joseph	Cohort	Early feeding reduced the risk of peanut sensitization among children with a parental history [adjusted OR, 0.2 (95% CI, 0.1,0.7); P = .007]. The relationship also became significant for egg when a cutoff for IgE of ≥ 0.70 IU/mL was used [adjustedOR, 0.5 (95% CI, 0.3,0.9)].	(87)
	Koplin	Case control	Introduction of cooked egg at age 4 to 6 months, vs later exposure reduced the risk of egg allergy [OR, 0.2 (95% CI, 0.06-0.71)].	(88)
	Des Roches	Case control	The reported consumption of peanuts during pregnancy and breastfeeding was higher in the case group (those who developed peanut allergy and associated with an increased risk of peanut allergy in offspring [OR, 4.22 (95%CI, 1.57,11.30) and OR, 2.28 (95% CI, 1.31,3.97) for pregnancy and breastfeeding, respectively].	(89)

	Sicherer	Case control	Multivariate analysis including clinical, laboratory, and demographic variables showed frequent peanut consumption during pregnancy {OR, 2.9(95% CI, 1.7,4.9)] to be associated with peanut IgE \geq 5 kUA/L.	(90)
Food processing	Chung	Laboratory analysis	After curing and roasting, mature peanuts exhibited approximately 20% higher levels of advanced glycation end adducts and higher IgE binding vs immature peanuts.	(91)
	Yadzir	Laboratory analysis	Extracts from raw shrimp bound higher IgE than extracts from boiled shrimp, but the purified boiled tropomyosin (the main shrimp allergen) demonstrates higher IgE binding vs raw shrimp.	(92)
	Samson	Laboratory analysis	Thermal processing can lead to the formation of new antigenic structures.	(93)
Vitamin D	Milner	Cohort	Early vitamin D use (within the first 6 months of life) was associated with a higher risk for food allergies in the exclusively formula-fed population [OR,1.63(95% CI,1.21,2.20)]. Vitamin use at 3 years of age was associated with increased risk for food allergies but not asthma in both breastfed [OR,1.62(95% CI,1.19,2.21)]and exclusively formula-fed infants [OR, 1.39(95% CI,1.03,1.88)].	(63)
	Cramago	Ecologic study	Strong north-south gradient for the prescription of EpiPens in the United	(60)

			States, with the highest rates found in New England. [adjusted β for New England vs the rest of the US, 4.07 (95%CI, 2.77,5.36)]	
	Mulins et al	Ecologic study	Using multivariate analysis , EpiPen prescription rates were higher in southern latitudes (less sunlight) compared with northern regions [β , -19.22(95% CI, -26.71 , -11.73)].	(61)
	Mulins et al	Ecologic study	Southern latitudes were associated with higher hypoallergenic formulae prescription rates [beta, -147.98(95% CI,-281.83 , -14.14)].	(62)

OR, odds ratio;RR, Relative Risk; CI,confidence interval ;CMA, Cow's Milk Allergy

Appendix B. protocols.

Initial Egg Challenge/Desensitization doses ^{(12)*}:

Dose (n:0)	Mg egg protein	Dosage form
1	0.1	Excipient microcrystalline cellulose
2	0.2	” — —
3	0.4	” — —
4	0.8	” — —
5	1.5	” — —
6	3	” — —
7	6	” — —
8	12	Dose of the powder
9	25	” — —
10	50	” — —
11	75	” — —
12	100	” — —
13	125	” — —
14	150	” — —
15	200	” — —
16	250	” — —

17	300	” —
-----------	------------	----------------

Increasing doses are given approximately every 30 minutes. If the subject does not tolerate a given dose and symptoms are mild, then that dose or the previously tolerated one is repeated, and the protocol proceeds as outlined. If the subject experiences significant symptoms, then the protocol is stopped, and the highest tolerated dose is used as the starting daily dose.

Post – Escalation Egg challenge (Egg Protein):

Number of dose	Egg protein mg at each challenge dose	Cumulative dose
1	1mg	1
2	3mg	4
3	10mg	14
4	30mg	44
5	100mg	144
6	300mg	443
7	600mg	1043
8	1000mg	2043
9	2000mg	4043
10	2000mg	6043

10 doses of powdered Meringue given every 10 to 20 minutes in increasing amounts up to a total of 10 g of powdered egg white (6.04 g of egg protein which is equivalent to 1 egg).

Scale for Grading Reaction Severity and management

Score	Symptom	Action
Mild	Pruritus, Urticaria, Flushing, Rhinoconjunctivitis	Observe May give Antihistamine (e.g. Benadryl or Reactin as prescribed) Call Research Team Research team will evaluate if dose adjustment is needed and if next dose will be given at home or in hospital.
Moderate	Angioedema, Throat tightness, Gastrointestinal complaints (cramping, pain, vomiting, diarrhea) Respiratory symptoms (Cough, Mucous production)	Give epinephrine IM as per protocol Give Antihistamine (e.g. Benadryl or Reactin as prescribed) Seek urgent care (hospital emergency room) Call Research team To give next adjusted dose in hospital research unit (CIM)
Severe	Wheeze, Respiratory Distress Hypoxia, Cyanosis, Hypotension Circulatory collapse (Shock)	Give epinephrine IM as per protocol Give Antihistamine (e.g. Benadryl or Reactin as prescribed) Call 911 Seek urgent care (transfer to hospital emergency room) Call Research team; if the symptoms are not improving within 10 minutes of the first dose, instructions will be given from the team regarding use of a second dose of epinephrine.

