Desensitization will begin with combined challenge/rush desensitization. After placement of an intravenous catheter, 20 ml blood samples will be collected, skin prick test (SPT) to egg will be performed and 5 ml of saliva will be collected. These samples will be used to establish participants' baselines for the various biological markers being examined during the study. The modified challenge will begin with a first single dose of 0.1 mg of placebo, alternating with powdered egg white in the form of Meringue powder. After the initial dose, subjects will receive approximately doubling doses every 30 minutes until the highest tolerated single dose will be determined (see Appendix B for Challenge/Rush doses). For doses of 25 mg and greater, powdered meringue will be dispensed from individual preweighed containers.. After the initial dose, subjects will receive approximately doubling doses every 30 minutes until the highest tolerated single dose was determined. All doses will be mixed with an acceptable vehicle food chosen by the subject and his or her parent. Subjects treated for reactions will be observed for 2 hours, and if there is no evidence of an allergic reaction, they will be discharged home. Self-administered epinephrine will be provided to all patients' caregivers, along with instructions and indications for administration and education about the nature of possible reactions to OIT. To ensure there were no ill effects of the daily dosing, each subject will return to the CIM on the second day for an observed administration of the starting daily dose.

All challenges and escalation doses will take place in the Center of Innovative medicine (CIM) as is currently done for our milk and peanut desensitization study . The CIM services include equipment and medications required to monitor and treat potential reactions . The CIM nurse that will assist in the desensitization protocol is a nurse that has been trained to work in an intensive care unit. The patients will not be admitted, but will remain under observation for 7 h each day, with the possibility for increasing this period if required.

SPT with the allergens listed above will be performed on all patients before starting desensitization, and the tests will be repeated at 3, 6 and 12 months. Blood tests will be also performed to measure sIgE and sIgG, T cell phenotypes (including regulatory Tcells), salivary IgA and DNA methylation before desensitization, at 3 weeks and at 3, 6 and 12 months.

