Reactions during the desensitization protocol will be classified according to the categories proposed by Perry et al.⁽⁶⁹⁾: mild reactions are defined when symptoms are limited to the oral mucosa or the skin; severe reactions include cardiovascular or respiratory symptoms or involvement of any four systems; all other reactions will be classified as moderate, although we will consider isolated abdominal discomfort as mild when it lasted for 30 min or less (appendix C protocols).

Build-up phase

Subjects will begin daily home dosing based on the highest dose tolerated during the modified rush of powdered egg white in 1 to 2 tablespoons of baby food or other acceptable vehicle food. Home doses will be provided in individual pre-weighed containers, and subjects will be instructed to ingest 1 dose daily for 2 weeks. As long as

subjects tolerate current doses, the doses will be increased every 2 weeks (see dosing schedule Appendix B) until reaching 150 mg and then increased by 50 mg at each visit until reaching maintenance (300 mg). Dose escalations will be made at visits in the research unit to ensure that subjects tolerate increases, and subjects will be observed for at least 2 hours after increases for signs of clinical reactions. Subjects will be given diaries to track their dose-related symptoms during the study

The protocol will be individualized according to each patient's tolerance to egg:

- Mild allergic reactions will be treated when necessary and the regimen will be continued when the patient becomes asymptomatic. The previously tolerated dose will be repeated before resuming the process.

- Moderate reactions will be treated and desensitization would be restarted on the following day at the previously tolerated dose.

- Severe reactions will be treated with the necessary measures and in the appropriate department, followed by an assessment of whether to interrupt desensitization or reduce the dose on the following day to 1/10 of the dose that caused the reaction.

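### Appendix B's rush-day rule gives moderate and severe reactors the same starting dose; for a severe reaction this conflicts with the section 4 rule, whose scope is not stated

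*Combined protocol and SAP*

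**What the plan says.** Appendix B (Initial Egg Challenge/Desensitization doses) gives the rush day two branches. After mild symptoms a dose is repeated and escalation goes on. Otherwise: "If the subject experiences significant symptoms, then the protocol is stopped, and the highest tolerated dose is used as the starting daily dose".

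Section 4 (Desensitization to egg) brings every child back to the research unit (CIM) on day 2 to take that starting dose under observation. The Build-up phase text then takes the dose home: "Subjects will begin daily home dosing based on the highest dose tolerated during the modified rush of powdered egg white". The child takes it once a day for two weeks, and after that "the doses will be increased every 2 weeks (see dosing schedule Appendix B) until reaching 150 mg".

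The same Build-up phase text sets out what to do by grade of reaction. For moderate: "Moderate reactions will be treated and desensitization would be restarted on the following day at the previously tolerated dose". A severe reaction is treated, and then there must be an "assessment of whether to interrupt desensitization or reduce the dose on the following day to 1/10 of the dose that caused the reaction".

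The grading paragraph in section 4, just above the Build-up heading, says that "severe reactions include cardiovascular or respiratory symptoms or involvement of any four systems". The severity table in Appendix B puts "Respiratory symptoms (Cough, Mucous production" in its moderate row. The severe row of that table covers emergency treatment and contact with the team; it says nothing about the next dose or about whether to continue.

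**The concern.** For a moderate rush-day reaction the two rules agree: stop, and go back to the dose that was tolerated. For a severe reaction they part in two ways. Appendix B sets a higher next dose than the one-tenth option, and it asks nobody to judge whether the child should continue. Staff running the rush day from the Appendix B dose table could follow it exactly and still depart from section 4.

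The child concerned has just had a severe reaction, is due to be dosed the next day, and then faces two weeks of daily dosing at home. The two severity scales add to the difficulty, because a cough falls under severe respiratory symptoms on one and is moderate on the other. Staff cannot be sure which children should trigger the stricter rule.

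**Working it through.** The plan states no figure on this point, so there is none to reproduce. The check sets the rules side by side and applies both to the listed doses.

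**Rules**

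| Reaction on the rush day | Appendix B | Section 4, Build-up phase |
|---|---|---|
| Moderate | Highest tolerated dose | Previously tolerated dose, next day |
| Severe | Highest tolerated dose | Assess: interrupt, or one-tenth of the reacting dose, next day |

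That *significant* takes in both moderate and severe is an inference. It follows from the rule having only one other branch, for mild symptoms.

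**Inputs.** The 17 doses in Appendix B, in mg of egg protein: 0.1, 0.2, 0.4, 0.8, 1.5, 3, 6, 12, 25, 50, 75, 100, 125, 150, 200, 250, 300. Assumptions: all are active doses, and the step before the reacting dose was tolerated.

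**Dose ratio.** For a reaction at dose d(i), Appendix B gives d(i−1) and the section 4 reduction gives d(i)/10. The ratio is d(i−1) ÷ (d(i)/10), for i = 2 to 17.

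| Reaction at (mg) | Appendix B next dose | One-tenth | Ratio |
|---|---|---|---|
| 12 | 6 | 1.2 | 5.0 |
| 25 | 12 | 2.5 | 4.8 (lowest) |
| 50 | 25 | 5 | 5.0 |
| 100 | 75 | 10 | 7.5 |
| 150 | 125 | 15 | 8.3 (highest) |
| 300 | 250 | 30 | 8.3 (highest) |

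The Appendix B dose is thus 48% to 83% of the reacting dose, against 10%. At 0.1 mg no earlier dose has been tolerated, so no ratio exists.

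**Sensitivity.** If the reacting dose is read as the cumulative rush dose, with no repeats, the denominator is the running sum divided by 10. The ratio then runs from 250 ÷ (1299/10) = 1.9 to 0.1 ÷ (0.3/10) = 3.3. If dosing is interrupted there is no ratio.

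**Cost of reducing.** Assume one listed step every two weeks, no setbacks, and a restart at the nearest listed dose at or below one-tenth. This can be done for reactions at 1.5 to 300 mg.
- Reaction at 50 mg: restart at 3 mg (step 6) rather than 25 mg (step 9). That is 3 extra steps, or 6 weeks.
- Reaction at 300 mg: restart at 25 mg (step 9) rather than 250 mg (step 16). That is 7 extra steps, or 14 weeks.
- Over the whole range: 3 to 7 extra steps, or 6 to 14 weeks.
- Build-up to 300 mg from the reduced start: from 8 steps × 2 = 16 weeks (from 25 mg) to 16 steps × 2 = 32 weeks (from 0.1 mg).

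**The case against.** The strongest reply is that section 4 already settles the matter. It says "Desensitization will begin with combined challenge/rush desensitization", so the rush day is part of desensitization. The grading paragraph stands before the Build-up heading and applies to the whole desensitization protocol. The list of actions opens with words about the protocol in general, and its next-day wording suits supervised dosing on consecutive days. On that reading the assessment is already required.

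Much of this stands: the severe rule was probably meant to cover the rush day. But it is printed under the Build-up heading and no sentence gives its scope. If it covers the rush day, two instructions conflict for the same child. If it does not, the rush day has no separate rule for a severe reaction. Either way the text needs amending.

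The second reply is that safeguards limit the risk. A treated child is watched for 2 hours and goes home only if no sign of reaction remains, observation lasts 7 hours a day and can be extended, and the day-2 dose is one the child tolerated, given at the CIM. This also stands, and it lowers the stakes. None of these steps requires a decision on whether to continue or reduce before home dosing.

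Third, the Appendix B severity table seems written for reactions away from the unit, since it tells the reader to call the team and seek urgent care. That is a fair inference and weakens the point about the two scales. The rush-day rule still does not say which scale it uses.

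A reader might infer that the protocol has no rule for severe reactions, or that severe reactors go straight to unsupervised dosing. The documents support neither: section 4 has the rule, and day 2 is observed.

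**Conclusion.** The point holds as a conflict between two stated dosing rules for a child with a severe rush-day reaction. It should be fixed because it concerns the safety of children and the correction is short.

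Its size is a single-dose ratio of 4.8 to 8.3 (1.9 to 3.3 on the cumulative reading), and it applies only where reduction is chosen over interruption. A reader might take this as a five- to eightfold rise in risk. The documents do not support that: they compare no outcomes between the two starting doses and give no frequency of severe rush-day reactions. At most 17 randomised children start in the active arm.

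The conclusion rests on reading *significant* as moderate or severe, and on the absence of any sentence that makes one rule override the other. Confidence is medium, because the intended scope of the section 4 rule can only be inferred.

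**What to change.** Amend Appendix B in three respects:
- Limit the highest-tolerated-dose rule to moderate reactions, graded by the section 4 categories, which that section already applies to the desensitization protocol.
- State that after a severe rush-day reaction the section 4 severe rule applies.
- Require the investigator's decision, to interrupt or to reduce to about one-tenth of the reacting dose, to be documented before any day-2 dose.

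Leave rounding to the investigator. One-tenth equals a listed dose in only one of 17 cases (250 to 25 mg), and always rounding down can go as low as 6% of the reacting dose (6 mg after 100 mg). Leave very low reacting doses to the investigator too. One-tenth falls below 0.1 mg for reactions at 0.1 to 0.8 mg, but compulsory interruption there would go beyond the plan's own standard.

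The cost is a short protocol amendment and no extra patients. There are three downsides:
- Reduced children need more escalation visits: about 6 to 14 weeks more on the assumptions above. A build-up of 16 to 32 weeks still fits within the 1-year primary time point unless setbacks are long.
- A child interrupted and not restarted counts as a failure in the success rate. Each is 1/17 = 5.9 percentage points, if all 17 stay in the denominator.
- On the section 4 scale an isolated cough would count as severe, so more children would need the documented decision.

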Appendix C. Budget

Total budget estimate: 78,000CAD per year including:

	Estimate (CAD)	comment

Yearly salary for an undergraduate student for expenses related to training in Lab evaluation mechanisms for auto-immune urticaria detection	35,000	
Study coordinator	40,000	Yearly salary with benefits
Paediatric test center (70CAD for each blood sample)	3000	
Staining with monoclonal Abs	3000	
Use of FACS	3000	
CBA	3500	
Culture materials and stimulating material	3500	
Travel expenses for presentation of results in scientific conferences	5000	
	78,000	yearly

Appendix D Study Schema
